The UroNav fusion biopsy system until recently *only* allowed targeted prostate biopsy to be performed transrectally. With over 200 devices sold in the United States, UroNav is the most commonly used targeted biopsy system and has been extensively studied by the National Institutes of Health (NIH). UroNav requires pre-biopsy mpMRI for lesion(s) delineation, real-time TRUS registered to the mpMRI and electromagnetic tracking of biopsy needles for precise guidance. The actual working elements of the UroNav fusion biopsy system includes the UroNav mobile workstation cart, ultrasound cart and the electromagnetic field generator which connects to the patient bed by a mobile arm. The electromagnetic field generator in combination with a navigation sensor mounted to the TRUS transducer merges the mpMRI images with live TRUS guidance to accurately biopsy the prostate. As previously mentioned, UroNav provides support for transrectal biopsy procedures but *now* has the capability to perform biopsy via a transperineal approach. The UroNav fusion-guidance for transperineal biopsy requires the transperineal stepper which holds the TRUS probe and a standard biopsy grid plate equipped with UroNav universal sensors to precisely perform biopsies. Invivo supports both UroNav and DynaCad which UTMB has recently acquired and the Department of Radiology currently has been working with for many years, respectively. DynaCad is a software used in the radiology suite which exports diagnostic 3D information from a prior mpMRI exam to discern the prostate gland and MR-suspicious lesions. The transperineal approach (skin halfway between scrotum and anus) essentially eliminates the risk of sepsis and/or infection associated with transrectal prostate biopsy samples obtained through feces and rectal mucosa. Sepsis occurs in up to 3% of patients who undergo transrectal prostate biopsy (Table 1).¹²

Table 1. Signs and Symptoms of Sepsis¹²

General Fever (>38.3°C) Hypothermia (<36°C) Tachycardia >90/min Tachypnea Hypotension (SBP<90 mmHg) Altered mental status Significant edema or positive fluid balance Oliguria Ileus Altered mental status/lethargy
 
Laboratory Normal WBC with >10% immature forms Creatinine increase >0.5 mg/dL INR >1.5 or aPTT >60 secs

Thrombocytopenia (platelet count <100,000/mm³)
Hyperglycemia (plasma glucose >120 mg/dL) in the absence of diabetes
Hyperlactatemia (>1 mmol/L)

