No study has compared UroNav transperineal mpMRI-targeted versus standard transrectal prostate biopsy in the detection of prostate cancer.

The **hypothesis** being tested is that computerized fusion guided biopsy (**UroNav**) will increase detection of csPCa compared to standard biopsy (SB) (transrectal) alone. The primary end point will be the comparison of detection rates csPCa between arm A mpMRI+ and arm B (refer to figure on page 9). csPCa will be defined according to the Standards of Reporting for MRI-targeted Biopsy Studies (START) criteria for targeted biopsy Gleason Score ≥ 7 or maximum cancer core length (CCL) ≥ 5 mm and the updated Epstein criteria for SB (Gleason score ≥ 7 , PSA density ≥ 0.15 , Gleason score ≥ 2 positive cores, and bilateral cancer).^{2,3} The secondary end points will be (1) comparison of the overall detection rate of PCa and csPCa between arm A mpMRI+, arm A mpMRI-, and arm B and (2) comparison of complication rates (Table 2) between arm A mpMRI+ and arm B.

Considering 10% of patients will be lost to follow-up, the total sample size needed will be 80 patients (See Section 9.1 Statistical Considerations). The clinical trial is enrolled in clinicaltrials.gov (**ClinicalTrials.gov Identifier NCT03044197**).

If the primary end point is reached, the study will continue and remain ongoing to examine the remaining secondary end points.

Specific Aims:

1. Determine if UroNav increases the detection of csPCa between arm A mpMRI+ than arm B standard transrectal biopsy.
2. Determine if UroNav increases the overall detection of PCa between arm A mpMRI+ versus arm A mpMRI- and arm B standard transrectal biopsy.
3. Determine if UroNav decreases rates of complications between arm A mpMRI+ than arm B standard transrectal biopsy.

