5.0 Study Procedures

Study population and design:

Eligible patients referred to the Division of Urology will be randomly assigned to one of the following arms: **arm A (mpMRI+ group)**, mpMRI prior to transperineal mpMRI-targeted prostate biopsy; **arm B (Standard group)**, TRUS-guided transrectal 12-core prostate biopsy.

In arm A, all patients with positive mpMRI evidence of lesions suspicious for PCa, i.e. PI RADS ≥ 3 will be submitted to transperineal MRI-targeted prostate biopsy (arm A mpMRI+). In cases of negative mpMRI results i.e. PI RADS < 3, arm A patients will

undergo TRUS-guided transrectal 12-core prostate biopsy (arm A mpMRI-)(refer to figure on page 9).

[figure not shown]
The present randomized clinical trial will compare the outcomes between the two arms.

Primary End-Points: The primary end point will be the comparison of detection rates csPCa between arm A mpMRI+ and arm B. csPCa will be defined according to the Standards of Reporting for MRI-targeted Biopsy Studies (START) criteria for targeted biopsy Gleason Score ≥ 7 or maximum cancer core length (CCL) ≥ 5 mm and the updated Epstein criteria for standard biopsy (Gleason score ≥ 7 , PSA density ≥ 0.15 , Gleason score ≥ 2 positive cores, and bilateral cancer).^{2,3} Patients will be enrolled in an intention to treat trial (See Section 9.1 Statistical Considerations).

Secondary End-Points: The secondary end points will be:

- i. Comparison of the overall detection rate of PCa and csPCa between arm A mpMRI+, arm A mpMRI-, and arm B and
- ii. Comparison of complication rates (Table 2) between arm A mpMRI+ and arm B.

If the primary end point is reached, the study will continue and remain ongoing to examine the remaining secondary end points.

Patients will be consented by Urology providers (IRB approved Co-Investigators and collaborators).

Randomization and data collection will be done by [REDACTED] [REDACTED] (study coordinator) into a REDCap generated case form (SEE APPENDIX). Study coordinator will provide de-identified data for statistical data analysis and will have master file, in password protected computer, which will link the PHI to subject ID (will be assigned by the study coordinator). After the completion of statistical analysis the master file will be deleted permanently.

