(PI). All patients will receive one dose fluoroquinolone antibiotic to be taken the morning of prostate biopsy (if fluoroquinolone allergy then may substitute Bactrim DS, if prior documented UTI(s) in past then antibiotic may be tailored according to those culture(s) sensitivities) to cover enteric flora. All patients will receive an enema until result to be performed the morning of prostate biopsy.

Urologists will obtain SOC informed consent and perform the TRUS biopsies.

The 12 cores will be obtained from 12 separate anatomical regions of the prostate which is standard practice in performing TRUS-guided transrectal prostate biopsy: left medial apex, left lateral apex, left medial midgland, left lateral midgland, left medial base, left lateral base, right medial apex, right lateral apex, right medial midgland, right lateral midgland, right medial base and right lateral base.

For arm A and arm B biopsy, [REDACTED] (the study research coordinator) , [name] and [name] (Chairman, Division of Urology and study co-investigator), will monitor safety and any possible Unanticipated Adverse Device Events (UADEs). Serious Adverse Events (SAEs), Adverse Events (AEs) and UADEs assessment will be done by [name].

For Arm A and Arm B biopsy, the procedure will be performed and the sample will be sent to the Pathology lab for analysis. [name] and other urology providers will not be involved with the sample analysis and biopsy report data and results. Once the report / data is available on Epic for review, the study coordinator will extract data from patient records/ Epic into an electronic data sheet (REDCap case form, SEE APPENDIX) on which the patient will be identified by a subject ID assigned to them, no PHI information will be present. The data analysis will be performed in aggregate. A master file linking the patient to Subject ID will remain with the study coordinator for data entry purposes and once the data analysis is complete, the master file will be securely stored and password protected.

- Adverse event assessment (Tables 2 and 3)

POST-PROCEDURE EVALUATION/ END OF STUDY- (Follow-up can be done by telephone or clinical visit)

- Diagnosis of csPCa- Based on the biopsy report will be available 2-4 weeks post-procedure
- Gleason score ((Grade System to classifying PCa)- Based on the biopsy report will be available 2-4 weeks post-procedure
- Total cancer core length (mm)- Based on the biopsy report will be available 2-4 weeks post-procedure

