- Maximum cancer core length (mm)- Based on the biopsy report will be available 2-4 weeks post-procedure
- Adverse event assessment- Can be done by telephone or clinical visit, usually 2-4 weeks post biopsy procedure

Table 2. Schedule of Events

Variables (Both Arm A and Arm B)	Pre-Study (within 2 months from consent and randomization)	Biopsy	Post-Biopsy Follow-up/Study End (within 2-4 wks from biopsy) Follow-up can be done by telephone or clinical visit)
Informed consent*	X		
Demographics	X		
Medical History	X		
Surgical History	X		
Clinical Stage/digital rectal exam	X		
Vital signs	X		
Height	X		
Weight	X		
PSA	X		
MRI PI-RADS (Arm A)	X	X	
Gland volume (MRI- Arm A or US- Arm B)	X	X	
Diagnosis of Prostate Cancer			X
Serum creatinine***	X		
Diagnosis of Clinically Significant Prostate Cancer**			X
Gleason score			X
Total cancer core length (mm)			X
Maximum cancer core length (mm)			X
UADE*		X	X

* Indicates study-only activity.

All other procedures/tasks are standard of care. Prostate specific antigen (PSA), Digital rectal examination (DRE), Prostate Imaging Reporting and Data System (PI-RADS), transrectal ultrasound (TRUS), Unanticipated Adverse Device Event

**Clinically significant PCa defined as targeted biopsy Gleason Score \geq or maximum CCL \geq 5 mm and the updated Epstein criteria for SB.

*** The serum creatinine assessment will be performed no more than one month prior to randomization.

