7.0 Adverse Events or Unanticipated Problems involving Risk to Participants or Others

Table 3. Complications associated with prostate biopsy

Common (greater than 1 in 10)	Occasional (between 1 in 10 and 1 in 50)	Rare (less than 1 in 50)

 •Blood in your urine for up to 10 days. •Blood in your semen for up to 6 weeks; this is harmless and poses no risk to you or any sexual partners. •Bruising in your perineal area. •Urinary infection (10% risk). •Sensation of discomfort due to bruising. •Haemorrhage(bleeding) preventing you from passing urine (2% risk). 	
 •Blood infection (septicaemia) needing hospitalisation (2% risk). •Haemorrhage (bleeding) needing hospitalisation (1% risk). •Failure to detect a significant cancer of the prostate. •The procedure may need to be repeated if the biopsies are inconclusive or your PSA level rises further. •Inability to pass urine (retention of urine). 	
 •Hospital-acquired infection •Colonisation with MRSA (0.9% - 1 in 110). •MRSA bloodstream infection (0.02% - 1 in 5000). •Clostridium difficile bowel infection (0.01% - 1 in 10,000). 
Please note: The rates for hospital-acquired infection may be greater in “high-risk” patients. This group includes, for example, patients with long-term drainage tubes, patients who have had their bladder removed due to cancer, patients who have had a

		long stay in hospital or patients who have been admitted to hospital many times.
--	--	----------------------------------------------------------------------------------

Complications associated with MR-Gadolinium:

The contrast material used in MRI called gadolinium is less likely to produce an allergic reaction than the iodine-based materials used for x-rays and CT scanning. Very rarely, patients are allergic to gadolinium-based contrast materials and experience hives and itchy eyes. Reactions usually are mild and easily controlled by medication. Severe reactions are rare.

Nephrogenic systemic fibrosis (NSF), a thickening of the skin, organs and other tissues, is a rare complication in patients with kidney disease that undergo an MR with contrast material. Gadolinium-based contrast material may be withheld in some patients with severe kidney disease.

Adverse Event:

For the purposes of this study, pre-planned interventions noted at baseline are not considered AEs.

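### Aim 3 has no workable complication outcome: endpoint (ii) cites the Schedule of Events, the only complication list (Table 3) includes diagnostic failures, and the event-collection rules may miss non-serious infections

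*Combined protocol and SAP*

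**What the plan says.** Aim 3 in Section 2.0 reads: "Determine if UroNav decreases rates of complications between arm A mpMRI+ than arm B standard transrectal biopsy". Section 5.0 gives the matching secondary endpoint (ii): "Comparison of complication rates (Table 2) between arm A mpMRI+ and arm B". The table with that number is headed "Table 2. Schedule of Events". Its only safety row is UADE, which Section 7.0 defines as serious effects not already identified in the plan by nature, severity or incidence.

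Section 5.0 lists, under the procedure visit, "Adverse event assessment (Tables 2 and 3". This is the only text that ties Table 3 to data collection. Table 3, in Section 7.0, is the only list of biopsy complications. It addresses the reader as the patient. Beside urinary infection (10%) and septicaemia needing hospitalisation (2%) it lists "Bruising in your perineal area", "Failure to detect a significant cancer of the prostate" and "The procedure may need to be repeated if the biopsies are inconclusive or your PSA level rises further".

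The safety rationale in Section 2.0 is narrower than the list: the transperineal route "essentially eliminates the risk of sepsis and/or infection associated with transrectal prostate biopsy samples".

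Section 7.0 restricts the adverse events collected to death and serious injury. Shortly afterwards it asks for all adverse events, with the non-serious ones entered on a spreadsheet. Follow-up is by telephone or visit, usually 2-4 weeks after biopsy. Section 9.0 describes an un-blinded trial and gives no sample size or power for Aim 3.

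**The concern.** Someone asked to carry out Aim 3 has no event set to count. The cited table leads to unanticipated device events, a category that largely shuts out complications the protocol already lists, such as sepsis and urinary infection. The other candidate, Table 3, was written to inform patients. Two of its items are not complications of a biopsy in any sense that can be scored here, and it sets frequent minor effects beside the infections that motivate the transperineal route.

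The larger risk is at data collection. A urinary infection treated without admission need not meet the death-or-serious-injury limit, so one statement in Section 7.0 leaves it out and the other takes it in. Staff know the arm, and the two biopsies are done in different settings (operating room and clinic). Recording could therefore differ by arm. An analyst can choose among recorded events later, but cannot recover events that were never asked about.

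**Working it through.** **Tracing the outcome**

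- *Endpoint (ii) to Table 2:* this gives UADE only. An event already described in the protocol does not qualify unless its severity or incidence is unexpected.
- *Adverse event assessment to Table 3:* this gives about 14 items, with no grading, no composite rule and no main item.
- *Missed significant cancer:* this needs a reference test after a negative biopsy, and none is planned.
- *Repeat procedure after a further PSA rise:* this depends on events after the study ends at 2-4 weeks.
- *Collection rules in Section 7.0:* septicaemia needing hospitalisation meets the SAE definition and is captured either way. Urinary infection managed without admission is captured under one statement and not the other.

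**Group sizes**

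The plan has no Aim 3 figure to reproduce, so I use the Section 9.0 numbers for Aim 2. There are 36 evaluable men per arm (72 / 0.90 = 80 enrolled). With 25% of arm A mpMRI-negative, mpMRI+ is 0.75 × 36 = 27. The comparison is 27 vs 36. The test is the planned two-sided 5% Fisher test, with power by full enumeration.

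**If Table 3 were pooled**

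This is my assumption; the plan does not say it. Rates printed in Table 3 are urinary infection 10%, septicaemia 2%, bleeding needing hospitalisation 1%, and bleeding that prevents passing urine 2%. (That last item is printed in the column for more than 1 in 10; I use the percentage.) The four minor items (blood in urine, blood in semen, bruising, discomfort) have only the column floor, so I take m = 10% to 30% each. Further assumptions are independent items, the same minor rates in both arms, and no urinary infection or septicaemia in arm A. The two diagnostic items and retention are left out because no rate is given.

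Any-event rate = 1 − product of (1 − rate).

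- m = 10%, arm B: 1 − 0.9⁴ × 0.90 × 0.98 × 0.99 × 0.98 = 43.9%
- m = 10%, arm A: 1 − 0.9⁴ × 0.99 × 0.98 = 36.3%; power 8%
- m = 30%, arm B: 1 − 0.7⁴ × 0.90 × 0.98 × 0.99 × 0.98 = 79.5%
- m = 30%, arm A: 1 − 0.7⁴ × 0.99 × 0.98 = 76.7%; power 4%

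**Infection only**

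Arm B: 1 − 0.90 × 0.98 = 11.8%, against 0% in arm A. With 0 of 27 events in arm A, Fisher's p is 0.065 at 5 of 36 and 0.033 at 6 of 36. Power is therefore P(X ≥ 6) for X ~ Binomial(36, 0.118), about 25%. Septicaemia alone at 2% gives 36 × 0.02 = 0.72 expected events in arm B and power below 0.1%.

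**If a missed cancer were scored as no csPCa found**

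Section 9.0 gives csPCa rates of 48% (mpMRI+) and 18.1% (arm B). The item would occur in 1 − 0.48 = 52.0% vs 1 − 0.181 = 81.9%, a gap of about 30 points in favour of arm A with 67% power at 27 vs 36. That is Aim 1 counted again as safety.

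**Can the pooled direction turn against arm A?**

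Suppose bruising, at rate b, occurs only with the transperineal route. After common factors cancel, arm A exceeds arm B only if 1 − b < 0.90 × 0.98 = 0.882, that is b > 11.8%. With all minor items at 10% the rates are 36.3% vs 37.6%, with no reversal. At 30% they are 76.7% vs 70.6%.

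**The case against.** - *Pooling is not in the plan.* Correct. A reader might infer from Table 3 that the trial will count a missed cancer as a complication and merge it with bruising and sepsis. No passage defines a composite or says how that item is scored, and the table reads as risk disclosure. The pooled figures show only what one permitted reading would do.
- *The list could make the safer arm look worse.* This is tempting but unsupported. Reversal needs an assumed excess of bruising in arm A above about 12%, and Table 3 gives no rates by route. Under the trial's own hypothesis the missed-cancer item works the other way and flatters arm A.
- *Items that cannot be observed add few events.* Largely true if they are left unscored. That is a reason to exclude them explicitly, since the only way to score a missed cancer from the data is as a negative biopsy.
- *The limit on adverse events may mean that minor effects are never collected, so no dilution arises.* True under the first statement in Section 7.0. Under that statement, non-serious urinary infections are also at risk of going unrecorded, which is worse for Aim 3.
- *The REDCap form may already itemise complications.* Possible. It is cited as an appendix that is not in the documents, so the fix is conditional on its content.
- *Naming an infection outcome does not rescue Aim 3.* This stands. Power is about 25% under the most favourable assumption of no infections in arm A.
- *The model is rough.* Also fair. Independence is doubtful (discomfort is listed as due to bruising), and the Table 3 rates are not specific to the transrectal route.

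**Conclusion.** The point holds as a defect of definition and data collection in a secondary endpoint. The wrong table reference, the two diagnostic items in the only complication list, and the conflicting collection rules can all be read directly in the text and rest on no assumption. Taken together, the trial as written may not record urinary infections evenly in its un-blinded arms.

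The dilution figures are conditional on pooling, independence, minor items at 10-30% and infection abolished in arm A. On those terms an 11.8-point infection difference becomes 7.5 points (43.9 − 36.3, before rounding) or 2.7 points (79.5 − 76.7, before rounding), and power falls from about 25% to 4-8%. The documents do not support the conclusion that the plan will hide or reverse the safety result. They support the narrower one that it leaves the outcome open, and that some of the permitted choices would be uninformative or would repeat the primary endpoint. It should be corrected, but it does not touch Aim 1.

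**What to change.** 1. Correct the table reference in endpoint (ii), in both Section 2.0 and Section 5.0.
2. Name urinary infection or septicaemia as the main complication outcome, and bleeding needing hospitalisation or urinary retention as the second.
3. Exclude the missed-cancer and repeat-procedure items from the complication outcome. They can stay in the patient information.
4. Report the expected minor effects item by item, descriptively.
5. Reconcile the two statements in Section 7.0 on which adverse events are collected.
6. Record each retained item as yes / no / not reached for every man in both arms at the existing 2-4 week contact.
7. Report differences with confidence intervals, and state in Section 9.0 that Aim 3 is not powered.

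The cost is protocol wording and, if the case form does not already have them, a few REDCap fields. No extra patients, visits or procedures are needed. The downside is that the headline complication outcome covers fewer event types.

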Adverse Events (AEs) collected in this study will be limited to death post biopsy procedure, serious injury (life threatening, results in permanent impairment of body functions or permanent damage to a body structure, or necessitates medical or surgical intervention to preclude permanent impairment of body functions),

Any unanticipated adverse device event will be recorded and reported to the IRB within 10 business days.

AE/SAE information must be collected up until subject's completion of the study. In the case of death or serious injury, Investigator or study coordinator must report to IRB as soon as possible within 10 business days after first learning the event.

Collection of all AEs, to be reported as follows:

- i) all serious adverse events and/or unanticipated problems involving subjects will be reported as required per the UTMB IRB Policies and Procedures, Section 8; and
- ii) All other adverse events will be recorded on an excel spreadsheet and submitted with each continuing review.

Serious Adverse Event (SAE):

An SAE is defined as an AE that meets one of the following conditions:

- Death during the period of protocol defined surveillance
- Life-threatening event (defined as a subject at immediate risk of death at the time of the event)
- An event requiring inpatient hospitalization or prolongation of existing hospitalization during the period of protocol defined surveillance
- Results in congenital anomaly or birth defect
- Results in a persistent or significant disability/incapacity
- Any other important medical event that may not result in death, be life threatening, or require hospitalization, may be considered a serious adverse experience when, based upon appropriate medical judgment, the event may jeopardize the subject and may require medical or surgical intervention to prevent one of the outcomes listed above. Examples of such medical events include allergic bronchospasm requiring intensive treatment in an emergency room or at home, blood dyscrasias or convulsions that do not result in inpatient hospitalization, or the development of drug dependency or drug abuse.

All SAEs will be:

- recorded on the appropriate SAE CRF
- followed through resolution by a study clinician
- reviewed and evaluated by a study clinician

Unanticipated Adverse Device Events (UADEs):

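### The complication endpoint cites the Schedule of Events instead of the complications table, and Section 7.0 contradicts itself on which adverse events are collected

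*Combined protocol and SAP*

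**What the plan says.** Aim 3 in Section 2.0 is to "Determine if UroNav decreases rates of complications between arm A mpMRI+ than arm B standard transrectal biopsy". It cites no table. The endpoint that serves it is stated twice, in Section 2.0 as "comparison of complication rates (Table 2) between arm A mpMRI+ and arm B" and in Section 5.0 as "Comparison of complication rates (Table 2) between arm A mpMRI+ and arm B".

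The table with that number is captioned "Table 2. Schedule of Events". It lists no complications. Its only safety row is UADE, which Section 7.0 defines as a serious device effect not already identified in the protocol, or another unanticipated serious device problem. The complications of biopsy are in Table 3 (Section 7.0). One line in Section 5.0 names both tables: "Adverse event assessment (Tables 2 and 3", closing the bracket there.

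On collection, Section 7.0 says "Adverse Events (AEs) collected in this study will be limited to death post biopsy procedure, serious injury". It explains serious injury as a life-threatening event, permanent impairment or damage, or an intervention needed to prevent permanent impairment. The sentence ends on a comma. The same section then calls for collection of all adverse events: serious ones go to the IRB, and the rest go on a spreadsheet submitted at continuing review. Its definition of a serious adverse event includes inpatient hospitalisation, which the limiting sentence does not mention.

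Section 5.0 schedules adverse event assessment at biopsy and, by telephone or visit, usually 2-4 weeks later. Section 9.0 gives no definition of a complication and no rate or power for Aim 3.

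**The concern.** An endpoint needs a list of events and a rule for collecting them. Here the cited list is a visit schedule, and the collection rule is stated in two ways that cannot both govern.

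This matters because Section 2.0 presents the transperineal route as one that "essentially eliminates the risk of sepsis and/or infection associated with transrectal prostate biopsy", and Aim 3 asks whether complications fall. Under the narrower rule, haematuria, haematospermia, bruising, discomfort and most urinary infections fall outside collection, which leaves rare serious events as nearly all there is to compare. Under the wider rule these events are recorded, but the only destination that Section 7.0 names for them is a continuing-review spreadsheet. Two staff members could follow the protocol in good faith and collect different data.

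**Working it through.** **No figure to reproduce.** The plan states no rate, effect size or power for complications. The check is textual, with some arithmetic for scale.

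**1. Table reference.** Both statements of the endpoint cite Table 2. Table 2 has a UADE row and no row for the adverse event assessment that Section 5.0 schedules. The UADE definition mainly excludes effects that the protocol already identifies, and so the Table 3 events at their listed severity and frequency. Taken literally, the endpoint counts almost none of the expected complications.

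**2. Table 3 against the limiting sentence.** Table 3 has 14 or 15 entries, depending on whether hospital-acquired infection is an entry or a heading. The classification that follows is an assumption of this review.
- Strict reading: 3 entries could qualify as death or serious injury (septicaemia needing hospitalisation, bleeding needing hospitalisation, MRSA bloodstream infection).
- Generous reading: 6 could, adding bleeding that prevents passing urine, urinary retention and *C. difficile* infection.
- Left out: from 14 - 6 = 8 of 14 (57%) to 15 - 3 = 12 of 15 (80%).
- Without the two entries that short follow-up cannot score (missed significant cancer, possible repeat biopsy): from 6 of 12 (50%) to 10 of 13 (77%).

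On every reading, the entries left out include haematuria, haematospermia, bruising, discomfort and, in general, urinary infection.

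**3. Scale for urinary infection.** Inputs: 36 men in arm B (Section 9.0, 72 patients, 36 per arm) and 10% (Table 3). Assumption: the rate, which is not arm-specific, applies to arm B.

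| Assumed rate p | Expected events, 36 × p | Chance of at least one, 1 - (1 - p)^36 |
|---|---|---|
| 5% | 1.8 | 1 - 0.95^36 = 0.842 |
| 10% | 3.6 | 1 - 0.90^36 = 0.977 |
| 15% | 5.4 | 1 - 0.85^36 = 0.997 |

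By comparison, Table 3's 2% for septicaemia needing hospitalisation gives 36 × 0.02 = 0.72 expected events.

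These rates serve for scale only. As the table reads here, a 2% item stands in the column for events above 1 in 10, which may come from reading the PDF.

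**4. Power with full capture.** Section 9.0 specifies Fisher's exact test, two-sided at 5%, and assumes about 25% of arm A is MRI-negative. That leaves 0.75 × 36 = 27 men in arm A mpMRI+ against 36 in arm B.
- 5 infections versus 0: p = [C(36,5) + C(27,5)] / C(63,5) = (376,992 + 80,730) / 7,028,847 = 0.065.
- 6 infections versus 0: p = [C(36,6) + C(27,6)] / C(63,6) = (1,947,792 + 296,010) / 67,945,521 = 0.033.
- With no infections in arm A mpMRI+, significance therefore needs at least 6 in arm B. At 10%, P(X ≥ 6), X ~ Bin(36, 0.10), is 0.145.
- At 10% versus 2%, power is 0.087.
- For septicaemia at 2% versus 0%, power is below 0.1%.

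**The case against.** The strongest reply is that both faults are clerical and the documents largely resolve them. Only one table is titled as complications of biopsy, Section 5.0 sends adverse event assessment to Tables 2 and 3 together, and Section 7.0 does order collection of all adverse events. The limiting sentence breaks off at a comma, so part of its list may be missing. The REDCap form, which sits in an appendix not available here, may already carry every Table 3 item.

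Much of this stands. A reader might infer that the protocol excludes most complications from collection, or that Aim 3's data will be lost. The documents do not support that: the contrary sentences are in the same section, and the form has not been seen. A reader might also infer that sepsis, the infection that Section 2.0 quantifies, would be missed. It would not, at least when it leads to admission. Section 7.0 requires every serious adverse event to be recorded on its own form, and hospitalisation is one of the criteria. The same holds for bleeding that needs admission. Nor does Aim 3 itself cite the wrong table; the endpoint text does.

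The reply does not remove the contradiction. A line that cites both tables does not correct two endpoint statements that cite one. No text says which of the two collection sentences prevails, which Table 3 rows count as complications, or that the non-serious events reach the analysis. A further fair point, that better capture would not make the infection comparison informative, is correct and is carried into the conclusion.

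**Conclusion.** The concern holds as an internal contradiction in a secondary endpoint, to be settled in the text. The endpoint refers to the wrong table in both places where it is stated, and Section 7.0 gives two incompatible collection rules. If the limiting sentence governs, most non-serious Table 3 complications would not be collected, while hospitalised septicaemia and bleeding would be. Loss of data is conditional on that reading and on the content of a form that was not available.

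The infection most exposed is non-serious urinary infection: 3.6 expected in arm B at 10% (1.8 to 5.4 at 5-15%), with a 98% chance of at least one (84-99.7%). This assumes that Table 3's rate applies to arm B and that most urinary infections are not serious; the documents do not give the share.

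A reader might also add up all the common Table 3 rows to claim a much larger loss in arm B. That is not supported, because two of those rows concern perineal bruising and discomfort from bruising, and arm B is transrectal.

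Correcting the text makes Aim 3 answerable as a description. It does not make it a test: power is about 15% for 10% versus 0% with 36 and 27 men. The change should be made, but the primary endpoint is not affected.

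**What to change.** 1. In Sections 2.0 and 5.0, point the complication endpoint to Table 3 and name the rows that count. Leave out the two that a 2-4 week contact cannot score (missed significant cancer, possible repeat biopsy). Table 3 gives up to 6 weeks for blood in semen, so score it as having occurred by that contact, not by duration.
2. In Section 7.0, reconcile the limiting sentence with the one requiring all adverse events. The result should be that the named complications are collected in both arms, at biopsy and at the existing 2-4 week contact, and that collection is no narrower than the section's own definition of a serious adverse event.
3. State that these data, and not only the continuing-review spreadsheet, feed the Aim 3 analysis.
4. State in Section 9.0 that Aim 3 is descriptive.

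Cost: protocol wording. If the REDCap form does not already list the named complications, add a short checklist at a contact that is already scheduled, with no extra visit. If it does, only the wording changes.
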